11.6. Safety Responsibilities

11.6.1. The Investigator

The Investigator's responsibilities include the following:

- Monitor and record all AEs, including SAEs, on the CRF regardless of the severity or relationship to study treatment.
- Determine the seriousness, relationship, and severity of each event.
- Determine the onset and resolution dates of each event.
- Monitor and record all pregnancies in female participants and follow up on the outcome of all pregnancies.
- Complete an SAE form for each SAE and fax or email it to the Sponsor within 24 hours of the site staff becoming aware of the event or according to national law.
- Pursue SAE follow-up information actively and persistently. Follow-up information
 must be reported to the Sponsor within 24 hours of the site staff becoming aware of
 new information or according to national law.
- Ensure all AE and SAE reports are supported by documentation in the participants' medical records.
- Pursue AE follow-up information, if possible, until the event has resolved or become stable. Record AE follow-up information, including resolution, on the CRF, as applicable.
- Report SAEs to local ethics committees, as required by local law.

11.6.2. The Sponsor

The Sponsor's responsibilities include the following:

- Before a site can enroll any participants, the Medical Monitor is responsible for reviewing with site staff the definitions of AE and SAE, as well as the instructions for monitoring, recording, and reporting AEs and SAEs.
- The Sponsor is to notify all appropriate regulatory authorities, central ethics committees, and Investigators of SAEs, as required by local law, within required time frames.

12. STATISTICAL METHODS AND DETERMINATION OF SAMPLE SIZE

12.1. General Considerations

The objectives of the study, the endpoints to be analyzed, and the statistical hypotheses are listed in Section 4.

In Part B, the primary endpoint and a subset of the secondary endpoints will compare the 50/28-mg Group to participants who received sham control in Study CS3B; these analyses will be performed using the 50/28-mg Group within this study and the data from the Study CS3B Sham Control Group. A matching algorithm will be used to select a group of participants who are similar to the 232SM203 higher dose group. The remaining secondary endpoints will compare the arms within Study 232SM203 Part B (50/28 mg Group versus 12 mg Group). This is detailed further in the following sections.

12.2. Analysis Sets

The ITT Set is defined as all participants who are randomized (or enrolled, as in Parts A and C) and receive nusinersen; participants will be analyzed in the treatment group to which they are randomized.

The Safety Set is defined as all participants who receive nusinersen; participants will be analyzed in the treatment group based on what they actually received.

The ITT, Safety, Sets will be defined separately for each of the following populations: Part A, Part B infantile-onset, Part B later-onset, and Part C.

A Per-Protocol Set will be defined for the Part B infantile-onset SMA population and will include the subset of the ITT Set who complete at least the initial 4 doses of drug/sham procedure, have a baseline assessment and at least a Day 183 efficacy assessment, and have no significant protocol deviations that would be expected to affect efficacy assessments.

The Matched Sham Set will be defined for the analysis of the primary and secondary endpoints comparing to sham. This will comprise of sham participants identified by the matching algorithm and all 50/28 mg participants in the ITT Set.

12.3. Definition of Baseline

The baseline for all assessments except CHOP-INTEND is defined as the last nonmissing assessment prior to the first dose of study treatment. The baseline for CHOP-INTEND is defined as the average of the assessments taken during the Screening/Baseline period.

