¹⁶Blood chemistry, hematology, and urinalysis samples will be analyzed by a central laboratory. For the Screening visit only, a local laboratory may be used instead for analysis, if needed, for the timely treatment of the participant at the discretion of the Investigator. If a local laboratory is used for the Screening visit, the samples should be collected on Day 1 for central laboratory evaluation (even if within 7 days of Screening). These assessments may be performed up to 7 days prior to dosing/study visit, if necessary. Urine total protein will be analyzed by local laboratory; however, if local analysis is not possible without a 24-hour urine collection, then samples will be analyzed by central laboratory. (Appendix B). Predose clinical safety laboratory assessments should be repeated when the assessment falls outside the protocol-specified window because of a delay in dosing. When the safety laboratory sample analysis is at risk due to logistical difficulties or issues with access to the central laboratory (e.g., due to COVID-19–related disruptions or humanitarian emergencies), these samples may be analyzed by the local laboratory. Any use of a local laboratory under these circumstances must be approved by the Sponsor prior to being implemented.

¹⁷Coagulation testing will be conducted locally at Screening and predose (within 7 days prior to dosing) at each dosing visit; results should be reviewed prior to dosing. Predose coagulation parameters should be repeated when the assessment falls outside the protocol-specified window because of a delay in dosing.

 18 A safety follow-up telephone call will be made 2 weeks (\pm 3 days) after the Day 29 dose for the first 20 participants.

²¹Videotaping of all motor milestone and motor function assessments is optional; however, if the participant/caregiver consents to video recording, all assessments should be recorded.

²²Two baseline assessments are required for CHOP-INTEND, HFMSE, and RULM. At least 1 assessment must be conducted during the Screening period. The second assessment may be conducted either during the Screening period or at Day 1 predose. If both baseline assessments are conducted during the Screening period, they should be completed on different days and the assessments do not need to be repeated on Day 1.

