- 4. Able to complete all study procedures, measurements, and visits and parent(s) or legal guardian(s)/participant has adequately supportive psychosocial circumstances, in the opinion of the Investigator
- 5. Must be compliant with the study travel policy (see Section 15.4)
- 6. Meets age-appropriate institutional criteria for use of anesthesia/sedation, if use is planned for study procedures (as assessed by the Investigator and either anesthesiologist or pulmonologist)
- 7. All female participants of childbearing potential (defined as any female physiologically capable of becoming pregnant) and all male participants of reproductive age must practice contraception as described in Section 11.5

Participants with SMA symptom onset ≤ 6 months (≤ 180 days) of age (infantile onset)

- 8. Age > 1 week to ≤ 7 months (≤ 210 days) at the time of informed consent
- 9. SMN2 copy number = 2
- 10. Onset of clinical signs and symptoms consistent with SMA at ≤ 6 months (≤180 days) of age
- 11. At Screening, receiving adequate nutrition and hydration, in the opinion of the Investigator
- 12. Body weight in at least the third percentile for age using appropriate country-specific guidelines
- 13. Gestational age of 37 to 42 weeks for singleton births and 34 to 42 weeks for twins. Infants with a lower gestational age may be considered for enrollment if there are no complications due to prematurity and approval by the Medical Monitor has been granted.

Participants with SMA symptom onset > 6 months (> 180 days) of age (later onset)

- 14. Onset of clinical signs and symptoms consistent with SMA at > 6 months (> 180 days) of age
- 15. Age 2 to < 10 years at the time of informed consent
- 16. Can sit independently but has never had the ability to walk independently
- 17. HFMSE score \geq 10 and \leq 54 at Screening
- 18. Estimated life expectancy > 2 years from Screening, in the opinion of the Investigator

Part C

All Participants

- 1. Signed informed consent of parent or guardian and signed informed assent of the participant, if indicated per participant's age and institutional guidelines
- 2. Currently on nusinersen treatment at the time of Screening, with the first dose being at least 1 year prior to Screening
- 3. Genetic documentation of 5q SMA (homozygous gene deletion, mutation, or compound heterozygote)

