- 4. Ability of the participant and/or his/her legally authorized representative (e.g., parent, spouse, or legal guardian), as appropriate and applicable, to understand the purpose and risks of the study, to provide informed consent, and to authorize the use of confidential health information in accordance with national and local privacy regulations
- 5. Able to complete all study procedures, measurements, and visits and parent(s) or legal guardian(s)/participant has adequately supportive psychosocial circumstances, in the opinion of the Investigator
- 6. Must be compliant with the study travel policy (see Section 15.4)
- 7. Meets age-appropriate institutional criteria for use of anesthesia/sedation, if use is planned for study procedures (as assessed by the Investigator and either anesthesiologist or pulmonologist)
- 8. All female participants of childbearing potential (defined as any female physiologically capable of becoming pregnant) and all male participants of reproductive age must practice contraception as described in Section 11.5
- 9. Postmenopausal female participants must be amenorrheic without an alternative medical cause and have a serum follicle-stimulating hormone level > 40 mIU/mL for $\ge 12 \text{ months}$

Escalating Dose and Randomized, Controlled Study of Nusinersen in SMA

prior to Screening or ≥ 6 weeks postsurgical bilateral oophorectomy (with or without hysterectomy) prior to Screening

Participants in Cohort 1

10. Males and females of any age (individuals \geq 18 years of age at Screening must be ambulatory)

Participants in Cohort 2

- 11. Males and females \geq 18 years of age at Screening (can be ambulatory) or nonambulatory)
- 12. HFMSE total score \geq 4 points at Screening
- 13. RULM entry item A score \geq 3 points at Screening

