Rationale: The 1-day visit windows for the Days 15 and 29 loading dose visits were clarified. For Part A, a 7-day window was added for the Day 64 visit, and in Part B, the Day 64 visit window was increased from 1 day to 7 days to offer greater visit scheduling flexibility for the sites and study participants with no anticipated impact on patient safety or quality of efficacy data collected.

This change also affects Section 1.1, Synopsis; and Section 5.2, Study Duration for Participants.

Section 1.3, Schedule of Activities

Change: A footnote was added to Tables 1, 2, and 3 in order to ensure that efficacy assessments (CHOP INTEND, HFMSE, and RULM) are conducted twice prior to the first dose of study treatment.

Now reads:

Table 1: Schedule of Activities for Part A

Footnote 20: Two baseline assessments are required for HFMSE and RULM. At least 1 assessment must be conducted during the Screening period. The second assessment may be conducted either during the Screening period or at Day 1 predose. If both baseline assessments are conducted during the Screening period, the assessments do not need to be repeated on Day 1.

Table 2: Schedule of Activities for Part B

Footnote 21: Two baseline assessments are required for CHOP INTEND, HFMSE, and RULM. At least 1 assessment must be conducted during the Screening period. The second assessment may be conducted either during the Screening period or at Day 1 predose. If both baseline assessments are conducted during the Screening period, the assessments do not need to be repeated on Day 1.

Table 3: Schedule of Activities for Part C

Footnote 22: Two baseline assessments are required for CHOP INTEND, HFMSE, and RULM. At least 1 assessment must be conducted during the Screening period. The second assessment may be conducted either during the Screening period or at Day 1 predose. If both baseline assessments are conducted during the Screening period, the assessments do not need to be repeated on Day 1.

Rationale: The requirement to assess efficacy twice prior to the first dose of study treatment was added to establish a more stable baseline and to be consistent with historical studies for nusinersen

Section 1.3, Table 1: Schedule of Activities for Part A

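### Two pre-dose HFMSE and RULM assessments are required, but Section 12.3 averages only CHOP-INTEND, so the earlier HFMSE or RULM score does not enter change from baseline

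*Protocol*

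**What the plan says.** In Section 1.3, Table 1 footnote 20 (Part A) and Table 4 footnote 22 (Part C Cohort 2) state: "Two baseline assessments are required for HFMSE and RULM". Table 2 footnote 22 (Part B) and Table 3 footnote 23 (Part C Cohort 1) make the same demand and add CHOP-INTEND to the list. At least one assessment must fall in Screening. For the other: "The second assessment may be conducted either during the Screening period or at Day 1 predose". In Parts B and C, two assessments done in Screening must be on separate days; the Part A footnote has no such condition.

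The Version 3 amendment summary gives the reason for a requirement that is still in force: "The requirement to assess efficacy twice prior to the first dose of study treatment was added to establish a more stable baseline". It adds a second reason, consistency with earlier nusinersen studies.

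Section 12.3 then sets two rules. For one scale: "The baseline for CHOP-INTEND is defined as the average of the assessments taken during the Screening/Baseline period". For everything else: "The baseline for all assessments except CHOP-INTEND is defined as the last nonmissing assessment prior to the first dose of study treatment". HFMSE and RULM fall under the second rule.

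Change in HFMSE and in RULM are the first two secondary endpoints listed for Part B later-onset and for Parts A and C (Section 4). Neither appears in Table 8. Section 12.4.3 reports such endpoints with summary statistics, and Section 12.11 says that groups other than Part B infantile-onset were not sized on statistical grounds.

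**The concern.** One data-collection requirement, written in the same words for three scales, is analysed in two ways, and no reason is given for the difference. The stated aim was a steadier baseline. For HFMSE and RULM a last-value rule gives no gain in stability, because the change score still rests on one pre-dose score with its full measurement error.

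The groups concerned are small: 8 and 16 participants in Part B later-onset, 6 in Part A, and up to about 40 in Part C. Section 12.11 says that the Part B later-onset group is there to explore safety, tolerability and efficacy, so the precision of the estimates is much of what its efficacy data can offer. Families are asked for a second assessment whose main benefit the analysis does not use.

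**Working it through.** **Plan's own figure.** None depends on the HFMSE or RULM baseline. The only powered endpoint is CHOP-INTEND (difference 24, SD 8.8, 50 against at least 20, two-sided 0.05). A simple two-mean calculation that ignores the survival component gives power above 0.999, in line with the stated figure of at least about 99%. The CHOP-INTEND baseline is already an average, so this point leaves that power untouched.

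**Which score is used.** With both scores present, the last nonmissing rule gives the later score weight 1 and the earlier score weight 0. The mean would give each 0.5. With one score missing, both rules use the score that exists.

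**Variance of change.** Let e be the error variance of one assessment and T the SD of true change. Take errors as independent and the true score as stable between the two pre-dose assessments.
- Single baseline: Var = T² + e + e = T² + 2e
- Mean of two: Var = T² + e + e/2 = T² + 1.5e
- Error part: (2 − 1.5)/2 = 25% lower

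**Assumed inputs.** The protocol gives no test-retest error for either scale. Assume a between-subject SD of 10, so that e = (1 − ICC) × 100, with ICC 0.90 to 0.97 (e = 10 to 3) and T = 3 to 5 points. With r the proportional fall in variance, the equivalent gain among the 24 Part B later-onset participants is 24/(1 − r) − 24.

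| ICC | T | Single | Mean of two | Variance falls | SD falls | Extra participants |
|---|---|---|---|---|---|---|
| 0.90 | 3 | 9 + 20 = 29 | 9 + 15 = 24 | 17.2% | 9.0% | 5.0 |
| 0.90 | 5 | 25 + 20 = 45 | 25 + 15 = 40 | 11.1% | 5.7% | 3.0 |
| 0.97 | 3 | 9 + 6 = 15 | 9 + 4.5 = 13.5 | 10.0% | 5.1% | 2.7 |
| 0.97 | 5 | 25 + 6 = 31 | 25 + 4.5 = 29.5 | 4.8% | 2.5% | 1.2 |

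**Scale-free form.** With R = T²/e, the variance falls by 0.5/(2 + R): 25%, 20%, 17%, 12.5% and 8% for R = 0, 0.5, 1, 2 and 4. The SD falls by about 13%, 11%, 9%, 6.5% and 4%. This form needs no between-subject SD, so it serves for RULM as well.

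**In points.** For illustration only, since Section 12.4.3 specifies no such interval: a 95% half-width for 8 against 16 is 1.96 × √(1/8 + 1/16) = 0.849 SD. It goes from 0.849 × √29 = 4.57 to 0.849 × √24 = 4.16 in the first row, and from 0.849 × √31 = 4.73 to 0.849 × √29.5 = 4.61 in the last.

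**Correlated errors.** If the two pre-dose errors have correlation ρ, the mean-of-two variance is T² + (1.5 + ρ/2)e, so the saving shrinks by the factor (1 − ρ). At an assumed ρ = 0.5 the range of 4.8% to 17.2% becomes 0.75/31 = 2.4% to 2.5/29 = 8.6%.

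**The case against.** Section 12.3 is explicit and can be carried out. Taking the last pre-treatment value is an ordinary definition, and CHOP-INTEND, as the primary endpoint, is a natural exception. That stands: the protocol does not contradict itself on how to compute the baseline. The rule simply does not serve the stated purpose of the second assessment.

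A reader might infer that the second measurement is collected and discarded. The documents do not support this. The later score is the baseline, and the earlier one is left out. Nor is the earlier score useless. It stands in if the later one is missing, and a Screening score decides eligibility for HFMSE in Part B later-onset (inclusion criterion 17) and for HFMSE and RULM entry item A in Part C Cohort 2 (criteria 12 and 13). Section 6.1 sets no such threshold for Part A, for Part C Cohort 1, or for RULM in Part B, so there only the fallback role remains.

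The second stated purpose, consistency with earlier nusinersen studies, also counts. The documents do not give the baseline rule those studies used for HFMSE and RULM, so they do not show whether averaging would match or depart from it.

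Finally, the size rests on assumed inputs and on independent errors. The two assessments are close in time, Sections 9.1.3 and 9.1.4 prefer the same evaluator, and Part A does not require separate days. Some correlation is plausible and would reduce the gain.

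**Conclusion.** The point holds as a low-cost gain in precision. The earlier HFMSE or RULM score carries no weight in change from baseline when both exist, although the pair was required to obtain a more stable baseline. Under the assumed values, averaging lowers the variance of change by about 5% to 17% and its SD by about 2% to 9%, equivalent to about 1 to 5 participants among 24. Correlated errors would make this smaller.

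A reader might infer bias, or a threat to the trial's main conclusions. Neither follows. Both Part B arms use the same rule, the endpoints are descriptive and outside the Table 8 sequence, and no stated power, sample size or alpha depends on them. Priority is modest.

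**What to change.** Reword Section 12.3 along these lines: *For CHOP-INTEND, HFMSE and RULM, baseline is the mean of the scores obtained in the Screening/Baseline period before the first dose, or the single score if only one exists; for every other assessment it is the most recent nonmissing pre-dose value.* The last-value baseline can stay as a sensitivity summary. If the sponsor prefers the last value, for instance for comparability with the earlier studies, Section 12.3 should say so and state what the other assessment is for.

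The cost is one sentence and matching derivation code; the assessments are already required. The rule should be settled before the data are analysed. Section 12.10 allows Parts A and C to be analysed before Part B is complete, so they come first.

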12.4. Methods of Analysis for Efficacy Endpoints

Within Part B to control the overall Type 1 error at a 2 sided alpha level of 0.05, a sequential testing procedure ranked in the order of the primary and secondary endpoints will be utilized. In this procedure, the primary endpoint of change in CHOP-INTEND total score from baseline to Day 183 for the Study CS3B Sham Control Group compared to the 50/28-mg Group will be tested. If this is statistically significant, then the first secondary endpoint of the proportion of motor milestone responders at Day 183 for the Study CS3B Sham Control Group compared to the 50/28-mg Group will be tested and so forth in the order of the remaining endpoints as detailed in Table 8. Inferential conclusions about each successive analysis require statistical significance of the prior one.

The statistical testing of the primary endpoint and a subset of secondary endpoints will use the Sham Control Group from Study CS3B. Within Study CS3B, there are 37 participants with an opportunity to attend the Day 183 visit.

algorithm will be used to select a group of snam participants from the pool of 37. The algorithm will attempt to match the largest number of participants and if unsuccessful, smaller pools will be selected and the minimum matched will be 20 participants.
The main analysis for the primary endpoint and secondary endpoints comparing nusinersen 50/28 mg to sham will be performed using the 50/28 mg participants in the ITT Set and the set of at least 20 sham participants selected via the matching algorithm.
The main analyses for secondary endpoints comparing 50/28 mg to 12 mg will be performed using the ITT Set.

12.4.1. Analysis of the Primary Endpoint in Part B

CHOP-INTEND

The primary efficacy endpoint of change from baseline to Day 183 in CHOP-INTEND total score will be analyzed using the joint-rank methodology to account for mortality [Berry 2013]. This joint-ranking procedure allows for a statistical test of the treatment effect on the CHOP-INTEND total score while accounting for loss of data due to deaths. In this analysis, a participant's Combined Assessment of Function and Survival score will be calculated by comparing each participant to every other participant in the study, resulting in a score of +1 if the CONFIDENTIAL

outcome was better than the participant being compared, -1 if worse, and 0 if the same. The participant's score will then be calculated by summing up their comparison to all the other participants in the study. For example, if 2 participants complete the study up to Day 183, their comparison score will be based on the change from baseline in CHOP-INTEND total score at Day 183. A participant who dies prior to the Day 183 visit will rank lower than any participant who completes the study up to Day 183. Two participants who both die prior to the Day 183 visit will be ranked based on the time of death with longer time to death corresponding to the higher rank. Hence, in general, these comparisons will result in participants who die being assigned the worst scores and ranked according to the time of death. Multiple imputation will be utilized to impute a missing Day 183 value of CHOP-INTEND for participants who discontinued for a reason other than death or where it was not assessed. Participants who have an imputed or available Day 183 score will be ranked more favorably than participants who die. The ranked scores will be analyzed using an analysis of covariance model with treatment included as a fixed effect and adjusted for baseline CHOP-INTEND total score and disease duration.

The trimmed-means method [Permutt and Li 2017] will be performed as a supplementary analysis. The analysis will be performed treating all dropouts and deaths as bad outcomes and trimming them out with other observed bad outcomes to form balanced comparison groups. In the trimmed mean approach, response scores are ranked from best to worst, and participants who died are considered as having worse outcomes than those who survived and completed the study. All response scores in the treatment group with high mortality/dropout rate will be retained. In the treatment group with the higher survival/completion rate, only the same proportion (as the survival rate in the high-mortality group) of the top response scores will be retained. The trimmed-mean difference can be interpreted as the difference between the top fraction of responses between the 2 groups. An analysis of covariance model will be fitted to the trimmed sample, with treatment as a factor and adjusting for covariates of baseline score and disease duration to obtain the adjusted mean difference. The pvalue associated with the adjusted-difference test statistic will be calculated using a reference distribution generated by a rerandomization procedure.

